#### **1.** Project Objectives and Long-term Significance

Shoulder pain is the third most common type of musculoskeletal disorder after back and neck pain in primary care (Van Der Heijden, 1999; Steuri et al., 2017). The prevalence of shoulder pain has been reported between 7% and 26% in the general population, with a life prevalence of up to 67% (Luime et al., 2004). The most common cause of shoulder pain is subacromial pain syndrome (SAPS), accounting for 44-60% of all shoulder disorders (Van Der Windt et al., 1995). Pain caused by SAPS can cause functional impairment and heavy social burden (Littlewood et al., 2012). Before recommending surgery, exercise therapy should be used as the first choice to treat SAPS (Kromer et al., 2009; Diercks et al., 2014; Haik et al., 2016). Several systematic reviews suggested that supervised exercise therapy can effectively improve the function and pain of patients with SAPS (Haik et al., 2008; Kuhn, 2009), while several other systematic reviews illustrated that the equal effectiveness of supervised exercises and home-based exercises (Desmeules et al., 2003; Kromer et al., 2009). Supervised exercises therapy requires substantial and specific resources and may be difficult to apply clinically (Karlsson et al., 2014). Thus, a home-based self-training program may allow individuals to treat SAPS with affordable and easily accessible treatments.

The use of complementary and alternative medicine treatment is growing continuously (Su & Li, 2011). Yi Jin Bang is a form of mind-body exercise and was developed in Hong Kong in the 1950s based on the principle of traditional Chinese mind-body exercise "Yi Jin Jing". In Chinese, Yi means change, Jin means tendons and sinews, while Bang means stick. As with all other Chinese medical exercise, the focus of Yi Jin Bang is on the cultivation of Qi (energy), which is assumed to harmonize mind and body and so might reduce pain (Von Trott et al., 2009). After reorganizing by physiotherapists, Yi Jin Bang has now become an easy-to-learn exercise program. Many scientific studies have demonstrated the effectiveness of mind-body exercises on pain, such as yoga, Tai Chi, and Qigong (Rendant et al., 2011; Cramer et al., 2013; Hall et al., 2017). However, the efficacy of Yi Jin Bang exercise in SAPS

is not scientifically evaluated.

# **Objectives**

To compare the effectiveness of ten weeks of home-based Yi Jin Bang exercise, versus home-based stretching and strengthening exercise, and versus waitlist control on pain, disability, flexibility, and muscular endurance in adults with SAPS. This study hypothesized that home-based Yi Jin Bang exercise and home-based stretching and strengthening exercise have similar effects in reducing pain and disability and improving flexibility and muscular endurance for individuals with SAPS.

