on pain in patients with chronic shoulder pain, and improvements in the Qigong group were comparable with those in the supervised exercise therapy group. Besides, Skoglund et al. (2011) indicated that six weeks of video-based Qigong training can improve neck-shoulder pain compared with no treatment. In a recent meta-analysis by Hall et al. (2017), Tai Chi was found effective in the short time for reducing pain and disability in patients with arthritis. A meta-analysis by Cramer et al. (2013) evaluated the effectiveness of yoga on low back pain, which found strong and moderate evidence for short-term effects and long-term effects of yoga in the treatment of low back pain, respectively. Moreover, a randomized controlled trial found that nine weeks of supervised yoga training was effective in treating chronic neck pain (Michalsen et al., 2012). Up to date, no studies have evaluated the effectiveness of Yi Jin Bang on the treatment of SAPS. Therefore, the purpose of this study is to evaluate the effects of Yi Jin Bang exercise on adults with SAPS in terms of pain, disability, flexibility, and muscular endurance.

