# Participants

This study will recruit 18-65 years old adults with symptoms of SAPS. Participants will be eligible if they meet all the following criteria: (1) aged 18 to 65 years old; (2) pain during overhead activities; (3) pain during active movements of the shoulder; (4) pain in the last three months; (5) Hawkins-Kennedy impingement test positive; (6) painful arc test positive; (7) infraspinatus muscle test positive. Participants will be excluded if they exhibited any of following criteria: (1) a history of fracture-dislocation of the shoulder; (2) full-thickness rotator cuff tear; (3) a history of shoulder surgery; (4) inflammatory of the vertebrae; (5) shoulder trauma in the last month; (6) any physical treatment for shoulder pain in the past month. Eligibility will be determined by two licensed physiotherapists through performing the clinical examination prior to entry into the study. Participants in this study will be recruited through mass email. Before the study, participants will be provided with consent forms, and then sign them. They will also be told that they can withdraw from the study at any time.

In terms of sample size, the effect size of the ROM exercise on the Shoulder Pain and Disability Index (SPDI) score found in a previous randomized control trial is adopted (Heron et al., 2017). Therefore, based on the estimation of sample size by G\*Power (effect size: 0.5;  $\alpha$ : 0.05; power: 0.80), a sample size of 14 individuals per group will be needed. Considering a 20% drop rate, we estimated that 18 participants per group will be needed.

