#### **Statistical Analysis**

All values will be reported as mean  $\pm$  SD. Two-way analysis of variance (ANOVA) with repeated measure (2 times × 3 groups) will be used to analyze differences at baseline and at ten-week post-intervention. Differences between the change within each group will be examined by one-way ANOVA. Post hoc tests will be used when necessary, to verify the pair-wise differences between means. The  $\alpha$  level of p < 0.05 will be considered statistically significant for all comparisons. All statistical procedures will be performed by SPSS software.

- Bang, M., & Deyle, G. (2000). Comparison of supervised exercise with and without manual physical therapy for patients with shoulder impingement syndrome. *The Journal of Orthopaedic and Sports Physical Therapy*, 30(3), 126-137.
- Desmeules, F. H., Côté, C., & Frémont, P. (2003). Therapeutic Exercise and Orthopedic Manual Therapy for Impingement Syndrome: A Systematic Review. *Clinical Journal* of Sport Medicine, 13(3), 176-182.
- Diercks, R., Bron, Dorrestijn, Meskers, Naber, De Ruiter., Van Der Woude. (2014). Guideline for diagnosis and treatment of subacromial pain syndrome: A multidisciplinary review by the Dutch Orthopaedic Association. *Acta Orthopaedica*, *85*(3), 314-322.
- Ginn, K., & Cohen, M. (2005). Exercise therapy for shoulder pain aimed at restoring neuromuscular control: a randomized comparative clinical trial. *Journal of Rehabilitation Medicine*, 37(2), 115-122.
- Greving, K., Dorrestijn, Winters, Groenhof, Van Der Meer, Stevens, & Diercks. (2012). Incidence, prevalence, and consultation rates of shoulder complaints in general practice. *Scandinavian Journal of Rheumatology*, *41*(2), 150-155.
  Effectiveness of physical therapy treatment of clearly defined subacromial pain: A systematic review of randomised controlled trials. *British Journal of Sports*

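### The only stated hypothesis is that the two exercise programmes have similar effects, but the plan has only tests of difference and no margin or confidence-interval rule, so the similarity part can be contradicted but not supported

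*Combined protocol and SAP*

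**What the plan says.** The Objectives section of the combined protocol and SAP compares Yi Jin Bang with stretching and strengthening exercise "and versus waitlist control on pain, disability, flexibility, and muscular endurance in adults with SAPS". It then states a single hypothesis, about the two exercise arms only: "home-based Yi Jin Bang exercise and home-based stretching and strengthening exercise have similar effects in reducing pain and disability", and likewise for flexibility and muscular endurance. No hypothesis is stated against waitlist. The background section gives a broader aim: "the purpose of this study is to evaluate the effects of Yi Jin Bang exercise on adults with SAPS".

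The Statistical Analysis section plans a repeated-measures ANOVA (2 times by 3 groups) for differences at baseline and ten weeks. It adds: "Differences between the change within each group will be examined by one-way ANOVA". On pairwise comparisons it says: "Post hoc tests will be used when necessary, to verify the pair-wise differences between means". A p-value below 0.05 "will be considered statistically significant for all comparisons". On reporting it says "All values will be reported as mean" with SD; no confidence interval is mentioned.

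The sample size paragraph under Participants adopts "the effect size of the ROM exercise on the Shoulder Pain and Disability Index (SPDI) score" from a previous trial. It enters an effect size of 0.5, alpha 0.05 and power 0.80, and arrives at 14 per group, or 18 after allowing for 20% dropout. No section defines how close two effects must be to count as similar.

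**The concern.** Each planned test has a null hypothesis of no difference. Rejecting it for the two exercise arms would contradict the stated hypothesis. Failing to reject it leaves the question open, because the same result arises from truly similar programmes and from a sample too small to separate different ones. The most the plan can offer in favour of its own hypothesis is therefore a non-significant p-value.

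In a trial of this size that outcome is likely whether or not the programmes are similar. With no rule fixed beforehand, what counts as support for similarity would be decided after the data are seen. A reader could then be told that Yi Jin Bang performs like usual exercise therapy when the data are compatible with it being appreciably worse or better.

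**Working it through.** **Inputs.** From the sample size paragraph: 14 evaluable and 18 enrolled per arm, alpha 0.05, power 0.80, effect size 0.5. The documents give no SD, no correlation between baseline and week 10, and no margin. Results are therefore in SD units and cannot be converted to SPADI points. The 0.5 SD deficit, the correlations and the 0.5 SD margin used below are assumptions.

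**Step 1. Reproduce the plan's figure.** The metric of the effect size is not stated. Read as Cohen's f in a one-way, three-group F test, the noncentrality is f² × N = 0.25 × 42 = 10.5 at 14 per group. Power is 0.803 at 14 and 0.769 at 13, so 14 is reproduced. Then 14 / 0.8 = 17.5, rounded up to 18. A repeated-measures interaction with f = 0.25 and correlation 0.5 also gives 14. Both are tests of difference, so neither sizes a similarity claim.

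**Step 2. Precision of the exercise-arm difference.** The 95% half-width is t(0.975; 2n − 2) × √(2/n), in SDs of the analysed score.
- n = 14: 2.056 × 0.378 = 0.78
- n = 18: 2.032 × 0.333 = 0.68

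Pooling the error over all three arms gives 0.76 and 0.67, which is almost the same.

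**Step 3. What a non-significant result means.** For a true difference d, an unadjusted two-sided t test has noncentrality d / √(2/n). With d = 0.5 this is 1.32 at n = 14 and 1.50 at n = 18.

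| True difference | Non-significant, n = 14 | Non-significant, n = 18 |
|---|---|---|
| 0 | 95% | 95% |
| 0.5 SD | 75% | 69% |

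A non-significant result is the usual outcome in both rows, so it discriminates poorly between them. Any multiplicity adjustment in the post hoc tests would raise the 0.5 SD row further.

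**Step 4. What baseline adjustment does to the interval.** Take equal SDs at both times and correlation ρ. The change-score half-width is the Step 2 value times √(2(1 − ρ)). The baseline-adjusted half-width is about √(1 − ρ²) × t(0.975; 2n − 3) × √(2/n), ignoring chance baseline imbalance. At n = 14 the last two factors are 2.060 × 0.378 = 0.778. In raw-score SDs at 14 per arm:

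| Assumed ρ | Change score | Baseline-adjusted |
|---|---|---|
| 0.3 | 1.183 × 0.777 = 0.92 | 0.954 × 0.778 = 0.74 |
| 0.5 | 1.000 × 0.777 = 0.78 | 0.866 × 0.778 = 0.67 |
| 0.7 | 0.775 × 0.777 = 0.60 | 0.714 × 0.778 = 0.56 |

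Adjustment is never wider in this table and helps most when the correlation is low, but the interval stays wide.

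**Step 5. Would adding a margin be enough?** Suppose similarity required the 90% interval to lie inside an assumed margin of ±0.5 SD, with a true difference of exactly 0. The expected 90% half-width is 0.64 SD at 14 per arm and 0.56 SD at 18, already wider than the margin. Integrating over the SD estimate, the chance of success is 0.4% (n = 14) and 1.6% (n = 18). For 80% power that rule needs about 70 evaluable per arm.

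**The case against.** The strongest reply is that the similarity statement is an informal expectation. The documents use no equivalence or non-inferiority wording, the sample size is not a similarity calculation, and the study is motivated by the lack of any evaluation of Yi Jin Bang in SAPS. The comparison with waitlist, named in the objective, is one the planned tests can address. This stands, and it limits both the reach and the severity of the point. A reader might infer that the trial cannot answer its question; the documents do not support that.

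A reader might also infer that the investigators intend to treat a non-significant test as proof of similarity. The plan does not say so. The defect is that no rule exists, not that a wrong rule was adopted.

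Third, the hypothesis also implies that both programmes reduce symptoms, and tests against waitlist can speak to that. This is correct, so only the similarity part is untestable.

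Finally, group means and SDs might let a reader construct an interval later. If the SDs of change were reported this would help estimation. Without a margin fixed in advance it would still not be a confirmatory test of similarity.

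What survives is that the statement is the only hypothesis in the document, and that following the analysis as written leaves a non-significant p-value as its only possible support.

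**Conclusion.** The plan is wrong as written on this point and should be corrected. The similarity part of its only stated hypothesis can be refuted but not supported by the planned analysis. The half-widths (Step 2) rest only on the planned group sizes and a two-group t interval. The non-significance rates (Step 3) rest also on the illustrative 0.5 SD deficit, and the similarity-rule figures (Step 5) on an assumed margin. These last two illustrate the problem; they do not measure the true difference in this trial.

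It may be tempting to conclude that the hypothesis must be replaced by superiority over waitlist, with one primary outcome and a Holm adjustment. That does not follow from the missing similarity rule. Those are separate questions with their own trade-offs, and they are not part of this point.

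**What to change.** Amend Objectives and Statistical Analysis before outcome data are examined.

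1. Report the ten-week difference, Yi Jin Bang minus usual exercise therapy, adjusted for the baseline value already collected, with a 95% confidence interval. Label it as estimation.
2. State that a non-significant ANOVA or post hoc test will not be reported as evidence of similar effects. Reword the similarity hypothesis as an expectation to be estimated, not confirmed.
3. Only if a confirmatory similarity claim is kept: justify a margin in advance, require a stated confidence interval to lie inside it, and state the power of that rule at 14 to 18 per arm.

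Items 1 and 2 need no extra participants or measurements. The cost is giving up a confirmatory similarity claim that the trial could not have supported. Item 3 would in practice mean revisiting the sample size unless a wide margin could be justified.

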# Long Term Impact

The presence of pain in the shoulder can lead to limits on work and/or recreational and domestic activity, thus bring a heavy burden of disease to both the individual and society (Van Den Dolder et al., 2014). Among people with shoulder pain, SAPS has the highest prevalence (Van Der Windt et al., 1995). Although the effectives of non-surgical supervised exercise therapy on SAPS has been demonstrated (Haik et al., 2008; Kuhn, 2009), people begin to support the use of self-training as the cost of supervised exercise therapy increasing (Werner et al., 2002). As an easy-to-learn exercise, Yi Jin Bang exercise may be more economic and more flexible in space compared to supervised exercise protocols. Our empirical evidence accumulated from the feedbacks of Yi Jin Bang practitioners found the positive effect in treating SAPS, however, scientific evidence has yet to be confirmed from randomized controlled trial studies. If proven, Yi Jin Bang exercise can be recommended to patients and physiotherapists, as a low-cost, flexible and easy to learn exercise in the treatment of SAPS. In a long run, medical cost can be reduced, family economic burden can be lower, and the quality of life of people can be improved.

## 2. Background of Research

## Work done by others

Shoulder pain is one of the most frequent musculoskeletal pain, with the point prevalence has been reported between 7% and 26% (Luime et al., 2004). The cumulative incidence of shoulder pain in general medical practice is estimated to be 29.3 per 1000 patients-years (Greving et al., 2012). Shoulder pain can cause severe disability and loss of quality of life because it interferes with many activities of daily life (Ginn & Cohen, 2005). There is little information about the costs associated with healthcare use and lost productivity in patients with shoulder pain, but it is considered considerable (Kuijpers et al., 2006). Among the common causes of shoulder pain, SAPS is the most common cause, accounting for 44-60% of all shoulder pains (Van Der Windt et al., 1995). SAPS is characterized by pain and functional restrictions that are exacerbated with repetitive arm activities at or above shoulder level (Haik et al., 2016).

The main goals of treatment for patients with SAPS are to reduce pain-related common impairments and improve upper limb function (Steuri et al., 2017). It has been determined that 15-28% of patients with SAPS may eventually require surgery (Bang & deyle, 2000). Commonly prescribed conservative treatment for SAPS includes corticosteroid injections, non-steroidal anti-inflammatory drugs, stretching and strengthening exercises, and physical therapy modalities (Senbursa et al., 2007). No evidence is available to indicate that the effectiveness of surgery is better than conservative treatment for patients with SAPS (Kvalvaag et al., 2017). A systematic review by Haik et al. (2016) suggested that exercise therapy aimed at restoring flexibility and strength of scapular muscles and the rotator cuff should be recommended to the first-line treatment for patients with SAPS before undergoing surgical treatment. Besides, this systematic review indicated that low-level laser therapy, pulsed electromagnetic field and tape are ineffective in treating SAPS. In another meta-analytical study which investigated the effectiveness of conservative treatment for pain, function, and range of motion (ROM) in adults with SAPS (Steuri et al., 2017), there revealed

that exercise therapy should be considered for all adults with SAPS, and the addition of manual therapy, tape, laser and extracorporeal shockwave therapy might have a little benefit. In addition, the meta-analysis reported that nonsteroidal anti-inflammatory drugs or corticosteroid injection can be a useful alternative only when exercise therapy is not possible.

Exercise therapy is considered to be the most valuable method for treating shoulder disorders and is the cornerstone of physical therapy treatment (Van Der Heijden, 1999), with several systematic reviews have reported its clinically and statistically effects on pain and function in patients with SAPS (Kromer et al., 2009; Kuhn, 2009; Haik et al., 2016). It remains unknown whether exercise therapy should be performed with or without supervision (Van Den Dolder et al., 2014). Several systematic reviews indicated that supervised exercises are effective in improving pain and function in patients with SAPS (Kuhn, 2009; Abdulla et al., 2015; Haik et al., 2016), while several other systematic reviews concluded that home-based unsupervised exercises are as effective as supervised exercises (Desmeules et al., 2003; Kromer et al., 2009). However, supervised training requires substantial and specific resources and may be difficult to apply clinically (Karlsson et al., 2014). In addition, the increasing cost of supervised exercise therapy also supports the use of home-based self-training protocols (Werner et al., 2002).

The use of complementary and alternative medicine treatment is growing continuously (Su & Li, 2011). Yi Jin Bang exercise is a stretching exercise that is beneficial to the mind and body. It was created in the 1950s in Hong Kong, according to the principle of traditional Chinese mind-body exercise Yi Jin Jing. In Chinese, Yi means change, Jin means tendons and sinews, while Bang means stick. Although there is no scientific research evaluating the effects of Yi Jin Bang exercises on pain, there are many scientific studies that have examined the effects of other mind-body exercises (e.g., Qigong, Tai Chi, yoga) on pain. Rendant et al. (2011) reported that six months of supervised Qigong training was more effective than no treatment

on pain in patients with chronic shoulder pain, and improvements in the Qigong group were comparable with those in the supervised exercise therapy group. Besides, Skoglund et al. (2011) indicated that six weeks of video-based Qigong training can improve neck-shoulder pain compared with no treatment. In a recent meta-analysis by Hall et al. (2017), Tai Chi was found effective in the short time for reducing pain and disability in patients with arthritis. A meta-analysis by Cramer et al. (2013) evaluated the effectiveness of yoga on low back pain, which found strong and moderate evidence for short-term effects and long-term effects of yoga in the treatment of low back pain, respectively. Moreover, a randomized controlled trial found that nine weeks of supervised yoga training was effective in treating chronic neck pain (Michalsen et al., 2012). Up to date, no studies have evaluated the effectiveness of Yi Jin Bang on the treatment of SAPS. Therefore, the purpose of this study is to evaluate the effects of Yi Jin Bang exercise on adults with SAPS in terms of pain, disability, flexibility, and muscular endurance.

# 3. Research Plan and Methodology

This will be a three-arm parallel-group randomized controlled trial with blinded outcome assessors. The trial comprises ten weeks of intervention. Participants will be randomly assigned into one of the following three groups: Yi Jin Bang group (group 1), usual exercise therapy group (group 2), or waitlist control group (group 3). The Yi Jin Bang group will practice an active, low-intensity home-based Yi Jin Bang exercise routine. The exercise therapy group will do a home-based stretching and strengthening training program. Participants in the waitlist control group will remain on a waiting list and will be provided either Yi Jin Bang training or usual exercise therapy after ten weeks. Pain, disability, flexibility, and muscular endurance will be evaluated before treatment, after the first treatment session, and after ten weeks in all three groups.

# Participants

This study will recruit 18-65 years old adults with symptoms of SAPS. Participants will be eligible if they meet all the following criteria: (1) aged 18 to 65 years old; (2) pain during overhead activities; (3) pain during active movements of the shoulder; (4) pain in the last three months; (5) Hawkins-Kennedy impingement test positive; (6) painful arc test positive; (7) infraspinatus muscle test positive. Participants will be excluded if they exhibited any of following criteria: (1) a history of fracture-dislocation of the shoulder; (2) full-thickness rotator cuff tear; (3) a history of shoulder surgery; (4) inflammatory of the vertebrae; (5) shoulder trauma in the last month; (6) any physical treatment for shoulder pain in the past month. Eligibility will be determined by two licensed physiotherapists through performing the clinical examination prior to entry into the study. Participants in this study will be recruited through mass email. Before the study, participants will be provided with consent forms, and then sign them. They will also be told that they can withdraw from the study at any time.

In terms of sample size, the effect size of the ROM exercise on the Shoulder Pain and Disability Index (SPDI) score found in a previous randomized control trial is adopted (Heron et al., 2017). Therefore, based on the estimation of sample size by G\*Power (effect size: 0.5;  $\alpha$ : 0.05; power: 0.80), a sample size of 14 individuals per group will be needed. Considering a 20% drop rate, we estimated that 18 participants per group will be needed.

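### The plan hypothesises that the two exercise arms are similar but tests only for differences, and the stated 80% power does not cover similarity

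*Combined protocol and SAP*

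**What the plan says.** The protocol's methodology section states: "This will be a three-arm parallel-group randomized controlled trial with blinded outcome assessors". The arms are Yi Jin Bang, usual exercise therapy and waitlist. The Objectives section compares Yi Jin Bang with both other arms but states one hypothesis, that "home-based Yi Jin Bang exercise and home-based stretching and strengthening exercise have similar effects in reducing pain and disability", and extends it to flexibility and muscular endurance.

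The Participants section bases the sample size on "the effect size of the ROM exercise on the Shoulder Pain and Disability Index (SPDI) score found in a previous randomized control trial". It enters an effect size of 0.5, alpha 0.05 and power 0.80 in G*Power, concludes that "a sample size of 14 individuals per group will be needed", and raises this to 18 for 20% dropout. It does not name the G*Power test, the metric (d or f), the SD that scales the 0.5, or the comparison that is powered.

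The Statistical Analysis section plans a repeated-measures ANOVA with 2 times and 3 groups, and adds: "Differences between the change within each group will be examined by one-way ANOVA". It continues: "Post hoc tests will be used when necessary, to verify the pair-wise differences between means". Results below 0.05 "will be considered statistically significant for all comparisons". Neither the protocol nor its analysis section gives an equivalence or non-inferiority margin, or a test of either kind.

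**The concern.** A hypothesis of similarity needs a margin and an interval or test judged against it. Every test planned here has no difference as its null hypothesis. The only planned result that could be offered in support of the hypothesis is therefore a non-significant comparison of the two exercise arms. Small arms tend to give that result whether or not the exercises differ, so following the plan would let an uninformative null stand as a finding of similarity.

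The power statement does not help, because it is for detecting differences. It also leaves the reader unable to tell which difference. The wording describes the effect of one exercise, whereas the sample size matches a measure of spread across three group means.

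**Working it through.** **Inputs.** From the protocol: 3 groups, effect size 0.5, alpha 0.05, power 0.80, 14 per group evaluable, 18 recruited, 20% dropout. Assumed: equal allocation, equal SDs, and effects measured in SDs of change unless stated otherwise.

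**1. The plan's figures.** For a one-way ANOVA on change with f = 0.5, the noncentrality is λ = f² × N, with 2 and N − 3 degrees of freedom.

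| Per arm | N | λ | Power |
|---|---|---|---|
| 13 | 39 | 9.75 | 0.769 |
| 14 | 42 | 10.5 | 0.803 |
| 18 | 54 | 13.5 | 0.902 |

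So 14 is the smallest size that reaches 80%. Dropout: 14 / 0.8 = 17.5, rounded up to 18. Both figures reproduce.

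**2. Is that the setting used?** Other readings of 0.5 at 80% power, two-sided:
- two-sample t test with d = 0.5: 64 per group;
- paired t test with d = 0.5: 34;
- 2 × 3 interaction with f = 0.5 and assumed correlation 0.5: 5 per group;
- 2 × 3 interaction with f = 0.25 and assumed correlation 0.5: 14 per group. Here λ = 0.0625 × 42 × 2 / 0.5 = 10.5 with 2 and 39 degrees of freedom, so this is the same effect as f = 0.5 on the change scale;
- repeated-measures between-group factor with f = 0.5: 14 per group only at an assumed correlation of 0.9, and it tests means averaged over time, not change.

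The exact matches for a test of change therefore all amount to f = 0.5 on the change scale. This is inference, since the plan does not say.

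**3. What f = 0.5 means.** If two arms are equal and the third lies d away, f = d√2/3. Then d = 0.5 × 3/√2 = 1.06 SD, the smallest best-to-worst range compatible with f = 0.5. With the third mean midway, the range is 0.5 × √6 = 1.22 SD.

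**4. Waitlist contrasts at that effect.** With equal exercise arms 1.06 SD better than waitlist and pooled error, the noncentrality is 1.06 × √(n/2). Power is 78% at 14 per arm and 88% at 18, unadjusted. With Bonferroni for three pairs it is about 62% at 14.

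**5. Exercise versus exercise.** The half-width of the 95% interval is t(0.975, 3n − 3) × √(2/n):
- 14 per arm: 2.023 × 0.378 = 0.76 SD;
- 18 per arm: 2.008 × 0.333 = 0.67 SD.

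Probability of a non-significant result, unadjusted:

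| True difference | 14 per arm | 18 per arm |
|---|---|---|
| 0.5 SD | 75% | 69% |
| 0.75 SD | 51% | 40% |

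**6. Equivalence power if the arms are truly equal.** This uses two one-sided tests at 5%. The margins are assumptions, because the plan gives none.

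| Margin | 14 per arm | 18 per arm |
|---|---|---|
| 0.5 SD | under 1% | 1% |
| 0.8 SD | 34% | 53% |
| 1.06 SD | 73% | 87% |

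**7. If 0.5 was not f.** Suppose both exercise arms are 0.5 better than waitlist.
- In SDs of change, f = 0.5 × √2/3 = 0.236. F-test power is 24% at 14 per arm and 31% at 18; a two-sample t test gives 25% and 31%.
- In baseline SDs, the effect on the change scale is 0.5/√(2(1 − r)), where r is the pre-post correlation. F-test power at 14 per arm is 14%, 24%, 38%, 54% and 85% for assumed r of 0, 0.5, 0.7, 0.8 and 0.9.

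**The case against.** The strongest reply is that the sample size is sound and the trial can do useful work. The 14 and 18 are correct for an F test that the plan includes. The objective also covers waitlist, and difference tests suit that comparison. At f = 0.5 the waitlist contrasts have reasonable power, at least unadjusted. All of this stands, but none of it reaches the hypothesis the plan actually states.

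A reader might infer that the trial has only about 25% power, because 0.5 is described as the effect of one exercise. The documents do not support that as a finding. They give no metric and no SD scale, and a direct calculation with d = 0.5 would give 64 or 34, not 14. The 25% holds only if 0.5 was meant as a mean difference in SDs of change. What stands is that the test and metric are not reported.

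A reader might also tie the similarity hypothesis to the Long Term Impact section: "If proven, Yi Jin Bang exercise can be recommended to patients and physiotherapists". In context, that sentence follows one on a positive effect in treating the condition, so it concerns efficacy. The recommendation does not rest on similarity to the other exercise, and the present point does not depend on it.

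Finally, the equivalence figures rest on assumed margins. That is so, but the interval widths and the non-significance rates need no margin.

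**Conclusion.** The point holds on any reading of 0.5. The stated hypothesis is similarity, the planned tests can only look for difference, and the 80% does not apply to it. The exercise-versus-exercise interval will extend about 0.76 SD either side at 14 per arm, or 0.67 SD at 18. A true difference of 0.5 SD would go undetected about three times in four, or 69% of the time with all 18 retained. These figures assume normal changes with equal SDs and pooled error.

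The sample-size arithmetic is not at fault. That the 80% belongs to a three-group F test with f = 0.5, and hence to a range of at least 1.06 SD, is a well-supported inference but remains an inference until the sponsor confirms it. The missing test and metric are a secondary reporting gap. The plan should be changed before analysis, because the change decides what the trial may conclude about the two exercises.

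**What to change.** Keep enrolment as it is and make three text changes.

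1. **Statistical Analysis.** Add: *The trial is not powered to show similarity of the two exercise arms. A non-significant difference between them will not be taken as similarity. The difference in change will be reported with its 95% confidence interval.*
2. **Objectives.** Reword the hypothesis so that the comparisons with waitlist are confirmatory and exercise versus exercise is estimation only. Without this, the first change would contradict the stated hypothesis.
3. **Participants.** Name the G*Power test and metric, and show how 0.5 follows from the cited effect. If it was f = 0.5, say that the 80% is for the three-group F test on change at a range of at least 1.06 SD. Add that, with equal exercise arms, each exercise-versus-waitlist contrast at 14 per arm has about 78% power unadjusted and about 62% with Bonferroni for three pairs. If 0.5 was a mean difference in SDs of change, state power of about 25% at 14 and 31% at 18 per arm. If it was in baseline SDs, state the assumed pre-post correlation and the power that follows.

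The cost is a few sentences, with no added participants or visits. The downside is that the stated power and the possible conclusion about the two exercise arms become less favourable, and the limited precision is disclosed, not removed.
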